Section 6.5.1 Allowed Medicine and Therapy Section 6.5.2 Disallowed Medicine and Therapy	Added "Prescription medications will be permitted during the study at the Investigator's discretion and recorded in the eCRFs" from Section 6.5.1 and removed "Use of nonprescription/over-the-counter medications, including herbal remedies and supplements, must be discontinued within 7 days before Day 1, except with prior approval from Alexion" from Section 6.5.2	ALXN1850 is unlikely to affect the PK of co-administered small molecules and vice versa, so permitting prescription medication at the Investigator's discretion should assist participant recruitment and retention. Also, these Sections had different wording regarding the use of herbal preparations and supplements in PA3, so they were combined in Section 6.5.1 of PA4	
Section 7.2 Participant Discontinuation/Withdrawal from the Study	Added the following: bullets for a positive drug (except prescription medications) or pregnancy tests during the study	For clarity and consistency within the protocol Site requested and Alexion approved For clarity and alignment within the protocol	

Section	Description of Change	Brief Rationale and/or Clarification	
	wording to the pre-existing bullet regarding a COVID-19 diagnosis that these participants will be evaluated for potential discontinuation from treatment and/or study according to the research site's COVID-19 protocol participants who miss a dosing visit or completes it out-of-window do not need to be withdrawn or discontinued from treatment but won't be considered "completed"		
Section 8.2.3 Electrocardiograms	Added "(all 3 should be performed sequentially within a 15-minute period)" after "The triplicates will be performed at approximately 1-minute intervals"	For clarity	
Section 8.5 Pharmacokinetics Section 8.6 Pharmacodynamics	Replaced specific collection windows with a statement to refer to the SoAs	To the reduce redundancy and the SoA is better designed to convey the nuances of this information	
Section 10.2 Clinical Laboratory Tests	Changed "central" to "local" in the 1 st bullet and deleted the 2 nd bullet	A local laboratory is used for safety laboratory tests	
	Modified the 6 th (now 5 th) bullet in Section 10.2 to match the SoA note (serum pregnancy test at Screening and urine pregnancy tests at subsequent timepoints)	For clarity, because the information in these 2 sections slightly conflicted in Protocol Amendment 3	
Section 10.2 Clinical Laboratory Tests, Table 6	Removed free hemoglobin, erythrocytes, corpuscular hemoglobin content, mean platelet volume, segmented (after neutrophils), urea, and PLP Removed tetrahydrocannabinol (cannabinoids) Added a footnote for glycated hemoglobin (HbA1c) to indicate that it only needs to be collected at Screening Added a footnote that clinical chemistry must be fasting only at Screening	These tests were determined redundant as the information they provide may be obtained from other laboratory tests already scheduled Recreational use of cannabis use is now legal in several US states and decriminalized/permitted for medicinal use in other states and countries (medicinal use of cannabis may relieve some symptoms of HPP). No drug interactions are anticipated with ALXN1850, given experience with asfotase alfa and its mechanism of action Clinically significant changes in HbA1c between the visits are not expected, and this will reduce participant/site burden For clarity	
10.4.2.1 Guidance for Female Participants	Modified the first sentence to indicate that a negative serum pregnancy test is required at Screening instead of within 1 day before the first dose mass index; ECG = electrocardiogram; eCR	To align with the SoA and the clarification noted above for Section 10.2	

Abbreviations: BMI = body mass index; ECG = electrocardiogram; eCRFs = electronic case report forms; ED = early discontinuationa; EoS = end-of-study; EoT = end-of-treatment; FDA = Food and Drug Administration; HPP = hypophosphatasia; P1NP = propeptide of type I procollagen PD = pharmacodynamics;

Page 95 of 97
Alexion Confidential

PK = pharmacokinetics; PLP = pyridoxal-5'-phosphate; sCTX = serum C-terminal Telopeptide of Type 1 Collagen; SoA = Schedule of Assessments; SRC = Safety Review Committee; ULN = upper limit of normal; VUS = variants of unknown significance

Page 96 of 97	
Alexion Confidential	

11. **REFERENCES**

- Hypersensitivity Reaction Labs

To the sites participating in the above named and numbered clinical study, this letter serves to inform you about the following administrative change to the above referenced protocol version.

• Clarifications in Section 1.3 Schedule of Activities, Table 1, 2 and 3: Postdose timepoints evaluation

This document provides clarification that all postdose timepoints are relative to the START of the IV infusion/injection (time 0) EXCEPT for ECG and PK/PD samples, performed/collected at EoI.

• Clarifications in Section 1.3 Schedule of Activities, Table 1, 2 and 3: Injection/infusion site evaluation

This document provides clarification on the timeframes for injection/infusion site evaluation. Injection/infusion site evaluations have to be performed from Time 0h and every 15 minutes (+ 5 minutes) until the 1st hr after the start of the injection/infusion. The rest of the timepoints have a window of \pm 15minutes.

• Clarifications in Section 1.3 Schedule of Activities, Table 1, 2 and 3: Hypersensitivity Reaction Labs

The Hypersensitivity Reaction labs have been clarified to reconcile the information from Table 1 and Table 2 with Table 3.

- If a hypersensitivity reaction is suspected, in general study overview for 1st and subsequent participants (table 1 and 2): hypersensitivity reaction labs (tryptase, IgE, C5b-9) as well as chemistry, hematology, and urinalysis samples should be collected as soon as possible (within 1 hour of the reaction) and again at 2 and 8 hours (+ 1 hour window each) after the 1st sample. The Day 1 predose samples will only be analyzed for participants with a reported suspected hypersensitivity reaction at any time following the first dose. If the participant is not in the clinic, these samples do not need to be collected and suspected hypersensitivity reaction persists beyond 8 hours, the CRU should contact the MM for guidance.
- If a hypersensitivity reaction is suspected, the day of the dosing (table 3): hypersensitivity reaction labs (tryptase, IgE, C5b-9) as well as chemistry, hematology, and urinalysis samples should be collected as soon as possible (within 1 hour of the reaction) and again at 2 and 8 hours (+ 1 hour window each) after the 1st sample. The Day 1 predose samples will only be analyzed for participants with a reported suspected hypersensitivity reaction at any time following the first dose.

Page 1 of 5 Alexion Confidential

Please file this letter and any IRB/EC correspondence with all copies of the protocol in the Investigator Site File and in all pertinent repositories in which the protocol is maintained. If there are any questions concerning these changes, please contact us. Applicable changes will also be captured in any future protocol amendment.

Phone:			
Email:			

Cc: eTMF

Page 2 of 5	
Alexion Confidential	

Table 1: Schedule of Activities - Study Overview for the First Participant in Each Cohort

Assessments	Screening			Treatment Period											EoT/ED Assessment	FU/ EoS Assessment							
Inpatient (I) or Outpatient (O) ^a	0	I/O	Ι	I	I/O	0	0	I/O	I	I	I/O	0	I/O	I	I	I/O	I	I	I/O	0	0	0	0
Study Day	-56 to -2	-1	1	2	2 3 5 8 14 15 16 17 19 21 22 23 28 29 30 31 36 51									65	85								
Hours postdose ^b				24	48	96	168			24	48	96			24			24	48	168			
Injection/ infusion site evaluation ^c				Х	Х		Х			Х	Х				Х			Х	Х	Х			
Hypersensitivity rxn labs (tryptase, IgE, C5b-9) ^d												← Se	e footi	note-"	X ⁿ –	→							
Chemistry, hematology, and urinalysis labs													← 2	$\langle n \rightarrow$									

^b All postdose timepoints are relative to the start of the IV infusion/time of the SC injection (ie, **T**time 0) except the **ECG**vital signs measurements, and PK/-and PD samples, and infusion site evaluation performed/collected at the EoI (see Table 3).

Error! Reference source not found. Injection/infusion site evaluations will be performed within 15 minutes (\pm 5 minutes) after injection/EoI and \pm 15 minutes of the timepoints. from Time 0h and every 15 minutes (\pm 5 minutes) until the 1st hr after the start of the injection/infusion. The rest of the timepoints have a window of \pm 15 minutes (see Table 3).

^d If the participant is in the clinic, collect the first sample ASAP (preferred) or within 1 hour of the suspected hypersensitivity reaction. The 2 subsequent samples also have a permitted + 1 hour window. If a hypersensitivity reaction is suspected, hypersensitivity reaction labs (tryptase, IgE, C5b-9) as well as chemistry, hematology, and urinalysis samples should be collected as soon as possible (within 1 hour of the reaction) and again at 2 and 8 hours (+ 1 hour window each) after the 1st sample. The Hypersensitivity rxn labs Day 1 predose samples will only be analyzed for participants with a reported suspected hypersensitivity reaction at any time following the first dose. If the participant is not in the clinic, these samples do not need to be collected and suspected hypersensitivity reaction will be reported as an AE only. If the suspected hypersensitivity reaction persists beyond 8 hours, the CRU should contact the MM for guidance.

Table 2: Schedule of Activities - Study Overview for Subsequent Participants in Each Cohort

Assessments	Screening			Treatment Period										EoT Assessments	FU/ EoS Assessments							
Inpatient (I) or Outpatient (O) ^a	0	I/O	Ι	Ι	I/O	0	I/O	Ι	Ι	I/O	0	I/O	Ι	Ι	I/O	Ι	Ι	I/O	0	0	0	0
Study Day	-56 to -2	-1	1	2	3	5	7	8	9	10	12	14	15	16	21	22	23	24	29	43	57	78
Hours postdose ^b				24	48	96			24	48	96			24			24	48	168			
Injection/infusion site evaluation ^c				Х	Х				Х	Х				Х			Х	Х	Х			
Hypersensitivity rxn labs (tryptase, IgE, C5b-9) ^d				$\leftarrow \underline{See \ footnote^d} \ \underline{X^n} \rightarrow$																		
Chemistry, hematology, and urinalysis labs												~	- X ⁿ →									

^b All postdose timepoints are relative to the start of the IV infusion/time of the SC injection (ie, **T**time 0) except the ECGvital signs measurements, and PK/ PD samples, and infusion site evaluation performed/collected at the EoI (see Table 3).

^cInjection/infusion site evaluations will be performed within 15 minutes (\pm 5 minutes) after injection/EoI and \pm 15 minutes of the rest of the timepoints. from Time/Oh and every 15minutes (\pm 5 minutes) until the 1st hr after the start of the injection/infusion. The rest of the timepoints have a window of \pm 15 minutes (see Table 3). ^d If the participant is in the clinic, collect the first sample ASAP (preferred) or within 1 hour of the suspected hypersensitivity reaction. The 2 subsequent samples also have a permitted \pm 1 hour window. If a hypersensitivity reaction is suspected, hypersensitivity reaction labs (tryptase, IgE, C5b-9) as well as chemistry, hematology, and urinalysis samples should be collected as soon as possible (within 1 hour of the reaction) and again at 2 and 8 hours (\pm 1 hour window each) after the 1st sample. The Hypersensitivity rxn labs Day 1 predose samples will only be analyzed for participants with a reported suspected hypersensitivity reaction at any time following the first dose. If the participant is not in the clinic, these samples do not need to be collected and suspected hypersensitivity reaction will be reported as an AE only. If the suspected hypersensitivity reaction persists beyond 8 hours, the CRU should contact the MM for guidance.

	Page 4 of 5
Alexion Confidential	

Assessments	Each Dosing Day (Inpatient Visits)									
Study Day (First Participant)	Days 1, 15, 22, 29									
Study Day for (Subsequent Participants)	Days 1, 8, 15, 22									
	Day 1 Each Dosing Day									
Day/Time	Only	Predose		Dose		Postdose ^a				
	Predose Per Window (if specified) -0.5 hr 0 hr EoI (IV Dose Only		EoI (IV Dose Only)	Every 15 min for 1st hr	2	6	12			
Injection/infusion site evaluation ^g				Х	X	Х	Х	Х	X	
Hypersensitivity reaction labs (tryptase, IgE, C5b-9, chemistry, hematology, and urinalysis)	Х		$\leftarrow \mathrm{X}^{\mathrm{i}} \!\rightarrow$							
Chemistry, hematology, and urinalysis labs						$\leftarrow X^i \!\! \rightarrow$				

Table 3: Schedule of Activities – Each Dosing Day for All Participants

^a All postdose timepoints are relative to the start of the IV infusion/time of the SC injection (ie, time 0 hr) except the ECG and PK/PD samples, and infusion site evaluation performed/collected at the EoI (see footnote d).

^g Injection/infusion site evaluations will be performed during the infusion, after I/EoI, and then within 15 minutes from Time/Oh and every 15 minutes (+ 5 minutes) until the 1st hr after the start of the injection/infusion. The rest of the timepoints have a window of \pm 15 minutes.

ⁱ If a hypersensitivity reaction is suspected, hypersensitivity reaction labs (tryptase, IgE, C5b-9 as well as chemistry, hematology, and urinalysis samples should be collected as soon as possible (within 1 hour of the reaction) and again at 2 and 8 hours (+ 1 hour window each) after the 1st sample. The Hypersensitivity rxn labs Day 1 predose samples will only be analyzed for participants with a reported suspected hypersensitivity reaction at any time following the first dose.

	Page 5 of 5	
 Alexion Confidential

eCRF	electronic case report form
HIV	human immunodeficiency virus
HPP	hypophosphatasia
ICF	informed consent form
IgG	immunoglobulin G
IQR	interquartile range
IV	Intravenous(ly)

MedDRA	Medical Dictionary for Regulatory Activities
n	number of non-missing values
N	number of participants
NAb	neutralizing antibody
P1NP	N-terminal propeptide of type I procollagen
PA	pyridoxic acid
PD	pharmacodynamic(s)
PEA	phosphoethanolamine
PK	pharmacokinetic(s)
PL	pyridoxal
PLP	pyridoxal-5'-phosphate
PPi	inorganic pyrophosphate
PT	preferred term
PTH	parathyroid hormone
Q1	quartile 1
Q3	quartile 3
QTcF	QT interval corrected for heart rate using Fridericia's formula
R	subcutaneous accumulation ratio
Rsq	the coefficient of determination
SAE	serious adverse event
SAP	statistical analysis plan
SC	subcutaneous(ly)
SD	standard deviation
SOC	system organ class
SRC	Safety Review Committee
t _{1/2}	apparent terminal elimination half-life
TEAE	treatment-emergent adverse event
TESAE	treatment-emergent serious adverse event
TNSALP	tissue-nonspecific alkaline phosphatase
T _{max}	time of maximum observed concentration
V _d	volume of distribution during the terminal phase
V _d /F	apparent volume of distribution during the terminal phase
%AUC _{extrap}	percentage of AUC _{inf} due to extrapolation
%CV	percent coefficient of variation
λ_{z}	terminal phase elimination rate constant

1. Introduction

Hypophosphatasia (HPP) is a rare, inherited, metabolic disease caused by deficient activity of the tissue non-specific isoenzyme of alkaline phosphatase, typically due to loss-of-function mutation(s) in the *ALPL* gene. ALXN1850 is an investigational enzyme replacement therapy that addresses the underlying cause of HPP by replacing the defective enzyme, thus reversing the mineralization defects of the skeleton and improving systemic manifestations of HPP.

The purpose of this statistical analysis plan (SAP) is to define the planned statistical analysis of the study data consistent with the study objectives. This SAP is written based on protocol ALXN1850-HPP-101, version Amendment 5, dated 11 Mar 2022. Any deviations/changes from the planned analyses described in this SAP will be identified, with justification, in the appropriate section of the clinical study report.

2. Objectives and Endpoints

The study objectives and corresponding endpoints are presented in Table 1.

Table 1: Objectives and Endpoints

Objective	Endpoints
Primary	
Assess the safety and tolerability of	Incidence of TEAEs and TESAEs
ALXN1850 given IV as a single dose and	
given SC 1 dose per week for 3 weeks	
Secondary	
Assess the PK of single IV and multiple SC	ALXN1850 PK (activity) over time profiles
doses of ALXN1850	and PK parameters
Assess the absolute bioavailability of	AUC _{tau} values of the first SC versus IV
ALXN1850 SC	administration
Assess the PD effects of single IV and	Absolute change and percent change from
multiple SC doses of ALXN1850	baseline in plasma concentrations of PPi and
	PLP and PLP/PL ratio over time
Assess the immunogenicity potential of	Incidence of ADAs and NAbs
ALXN1850	
Exploratory	
Explore role of ALXN1850 on calcium and	Absolute, change, and percent change from
bone homeostasis and other PD biomarkers	baseline in ionized Ca, phosphorus,
	magnesium, PTH, CTX-1 (sCTX), P1NP,
	osteocalcin, and PA over time

Abbreviations: ADA = antidrug antibody; AUC_{tau} = area under the plasma concentration versus time curve within the dosing interval; Ca = calcium; IV = intravenous; NAb = neutralizing antibody; P1NP = N-terminal propeptide of type I procollagen; PA = pyridoxic acid; PD = pharmacodynamics(s); PK = pharmacokinetic(s);

PL = pyridoxal; PLP = pyridoxal-5'-phosphate; PPi = inorganic pyrophosphate; PTH = parathyroid hormone;

SC = subcutaneous; CTX-1 (sCTX) = serum C-telopeptide cross-link of type 1 collagen;

TEAE = treatment-emergent adverse event; TESAE = treatment-emergent serious adverse event

3. Study Design

This is an open-label, dose-escalating study to assess safety, tolerability, PK, PD, bioavailability, and immunogenicity of ALXN1850 when given IV and SC to adults with HPP.

Study participants will be enrolled into 3 cohorts in a sequential fashion. The first participant in each cohort will begin dosing before the rest participants of the cohort. A Safety Review Committee (SRC) will convene after the first participant in each cohort has completed the first IV dose to assess safety and tolerability, and to endorse initiation of SC study drug administration to the first participant as well as IV and SC study drug administration to the remaining number of participants in the cohort. Once at least 3 participants in Cohort 1 participants have received a single IV dose and 3 weekly SC doses, the SRC will convene again to review safety and tolerability data, and to determine if the dose escalation may proceed. If the SRC endorses dose escalation, Cohort 2 will begin dosing at the next dosing level. Cohort 3 will begin dosing after the SRC has reviewed all relevant safety, tolerability, and PK data from participants in Cohorts 1 and 2 and endorsed dose escalation. The study design is presented in Figure 1.

Participants who are positive for ADAs at the last assessment of the study will be given options to enable further monitoring of their ADA values after the end of the study; these options may include enrollment in the Global HPP Registry.

4. General Statistical Considerations

All statistical analyses will be conducted using statistical analysis system SAS® Version 9.4 or higher (SAS Institute, Inc., Cary, North Carolina) and Phoenix® WinNonlin® Version 8.0 or higher (Certara USA, Inc., Princeton, New Jersey).

Descriptive statistics for continuous variables will include number of participants (N), number of non-missing values (n), a rithmetic mean, geometric mean (for PK analysis only), standard deviation (SD), pe rcent coefficient of variation (%CV; for PK analysis only), geometric %CV (for PK analysis only), median, quartile 1 (Q1, for safety analysis only), quartile 3 (Q3, for safety analysis only), i nterquartile range (IQR, for safety analysis only), minimum, and maximum, unless otherwise noted. For categorical variables, frequencies and percentages will be presented. Descriptive statistics will be summarized by cohort and overall and by timepoint, unless otherwise noted. In the case where N is an even number, the median will be calculated as the average of the 2 middle numbers of the ordered samples or parameter estimates.

For the summary statistics of all continuous variables unless otherwise specified, for absolute value, minimum and maximum will be presented to the same number of decimal places as the raw data, mean, median, Q1, Q3, and IQR will be presented to one more decimal places than the raw data, SD will be presented to two more decimal places than the raw data; for percent change, minimum and maximum will be presented to one decimal place, mean, median, Q1, Q3, and IQR will be presented to two decimal places, and SD will be presented to three decimal places. %CV and geometric %CV will be presented to one decimal place, and N and n will be presented to integer.

Percentages will be suppressed when the count is zero and will be presented to one decimal place. The denominator for all percentages will be the number of participants in the cohort for the population of interest, unless otherwise specified.

All tables, listings, and figures will be presented by cohort, unless otherwise specified.

All data listings will be sorted by cohort, participant number, and date-time if applicable.

No algorithm for imputation of missing data will be employed but will be analyzed as missing.

Study days are calculated with respect to the first dose date as below:

- If the assessment/observation date is on or after the first dose date, then Study Day = Assessment/Observation Date First Dose Date + 1;
- Otherwise, Study Day = Assessment/Observation Date First Dose Date

Study weeks are calculated with respect to the first dose for the assessment/observation occurred on or after the first dose as below, unless otherwise specified:

• Study Week = Integer part of (Assessment/Observation Date – First Dose Date)÷7+1

Baseline will be defined as the last non-missing assessment (including repeated and unscheduled assessments) before the first dose of study drug administration, unless otherwise specified.

For summary of safety assessments, if there are repeated measurements at a time point, the first non-missing assessment at that time point will be used in the summary tables.

Unscheduled results will not be included in the summary tables, except for determining Baseline, but will be presented in data listings.

For safety laboratory evaluations, for the purpose of summarization, any numeric values recorded below the lower limit or above the upper limit of quantification will be set to the respective limit for all related summaries. In listings, original results containing inequality sign will be displayed, unless otherwise specified.

The methodology and data handling specifications for PK data are detailed in Section 8.

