In a monkey 28-day toxicity study, administration of ALXN1850 via SC injection once q3d for 28 days (Days 1, 4, 7, 10, 13, 16, 19, 22, 25, and 28) for a total of 10 doses to male and female cynomolgus monkeys was well tolerated up to 20 mg/kg/dose, the highest dose evaluated in this study. There were no ALXN1850-related changes in injection site reactions (dermal scoring), body weights, body weight gains, qualitative food consumption, ophthalmology, manual respiratory rates, indirect blood pressures, qualitative electrocardiography, hematology, urinalysis, gross pathology, and organ weights. At the end of the dosing phase, there were dose-related increases in ALP activity (anticipated pharmacology effect) which were fully (1 mg/kg/dose) or mostly ($\geq 5 \text{ mg/kg/dose}$) resolved following a 28-day recovery period. Non-adverse ALXN1850 related microscopic changes were confined to the injection sites and included minimal to mild degeneration/necrosis, mineralization, and mixed cell inflammation/infiltration. Partial recovery of degeneration/necrosis and mixed cell inflammation/infiltration of the injection site(s) were observed within the recovery groups, while minimal to mild mineralization persisted in recovery males at $\geq 1 \text{ mg/kg/dose}$ and females at 20 mg/kg/dose. Heart rate increases were observed in all animals at 1 mg/kg/dose and in some of the animals at \geq 5 mg/kg/dose. Heart rate and electrocardiogram (ECG) values remained within a normal range of biological variation for monkeys of this age, and therefore these heart rate increases were not considered to be adverse, given the incongruity with systemic exposure data. In conclusion the dose level of 20 mg/kg/dose is considered to be the NOAEL that corresponds to Day 24 males and females combined mean C_{max} value of 254 µg/mL and mean AUC_{0-72h} value of 15400 h*µg/mL, respectively.

In conclusion, SC administration of ALXN1850 to rats or monkeys did not identify any new or unexpected systemic toxicity or local tolerability findings. The NOAEL dose of 20 mg/kg/dose from the ALXN1850 GLP monkey toxicity study was used to select the Phase 1 study starting dose. The observed exposure of the NOAEL at 20 mg/kg/dose from the GLP SC monkey toxicity

Page 32 of 97	
Alexion Confidential	

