8.3.6.2. Injection-associated Reactions

Injection-associated reactions are defined as systemic AEs (eg, fever, chills, flushing, alterations in heart rate and blood pressure, dyspnea, nausea, vomiting, diarrhea, and generalized skin rashes) occurring during or within 24 hours of the start of SC injection that are assessed by the Investigator to be related to the study drug. AE intensity reporting procedures are outlined in Section 10.3.4.

Page 54 of 97
Alexion Confidential

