Summary statistics and change from baseline for vital signs (temperature, respiratory rate, pulse, and systolic and diastolic blood pressure) will be presented by relative time to dose.

Vital sign measurement results, including height, weight, and BMI, will be presented in a data listing.

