9.5. Electrocardiograms

Electrocardiogram (ECG) parameters will include heart rate, PR, RR, QRS, QT, and QTcF intervals.

Triplicate 12-lead ECGs will be obtained at below timepoint and at screening:

First participant within each cohort	Subsequent participants within each cohor	
Day 1 (pre-dose, 2h, 6h, and 12h post IV	Day 1 (pre-dose, 2h, 6h, and 12h post IV	
dose)	dose)	
Day 2 (24 hours post IV dose)	Day 2 (24 hours post IV dose)	

First participant within each cohort	Subsequent participants within each cohort
Day 3 (48 hours post IV dose)	Day 3 (48 hours post IV dose)
Day 5 (96 hours post IV dose)	Day 5 (96 hours post IV dose)
Day 8 (1 week post IV dose)	
Day 15 (pre-dose, 2h, 6h, and 12h post SC	Day 8 (pre-dose, 2h, 6h, and 12h post SC dose
dose 1)	1)
Day 16 (24 hours post SC dose 1)	Day 9 (24 hours post SC dose 1)
Day 17 (48 hours post SC dose 1)	Day 10 (48 hours post SC dose 1)
Day 19 (96 hours post SC dose 1)	Day 12 (96 hours post SC dose 1)
Day 22 (pre-dose, 2h, 6h, and 12h post SC	Day 15 (pre-dose, 2h, 6h, and 12h post SC
dose 2)	dose 2)
Day 23 (24 hours post SC dose 2)	Day 16 (24 hours post SC dose 2)
Day 29 (pre-dose, 2h, 6h, and 12h post SC	Day 22 (pre-dose, 2h, 6h, and 12h post SC
dose 3)	dose 3)
Day 30 (24 hours post SC dose 3)	Day 23 (24 hours post SC dose 3)
Day 31 (48 hours post SC dose 3),	Day 24 (48 hours post SC dose 3)
Day 36 (1 week post SC dose 3)	Day 29 (1 week post SC dose 3)
Day 65/End of Treatment (EoT) (6 weeks	Day 57 EoT (5 weeks post SC dose 3)
post SC dose 3)	

Note: Predose triplicate 12-lead ECGs will be performed 3 times at approximately 2, 1, and 0.5 hours before the start of dosing.

The average of the triplicate ECG readings at the time points collected will be calculated and used in the summary statistics. The baseline will be defined as the average of the last non-missing assessment (including repeated and unscheduled assessments) before the first dose of study drug administration.

Relative time to dose will be presented for the summary statistics includes:

- Baseline, 2 hours post IV dose, 6 hours post IV dose, 12 hours post IV dose, 24 hours post IV dose, 48 hours post IV dose, 96 hours post IV dose, and 1 week post IV dose;
- Pre SC dose 1, 2 hours post SC dose 1, 6 hours post SC dose 1, 12 hours post SC dose 1, 24 hours post SC dose 1, 48 hours post SC dose 1, and 96 hours post SC dose 1;
- Pre SC dose 2, 2 hours post SC dose 2, 6 hours post SC dose 2, 12 hours post SC dose 2, 24 hours post SC dose 2;

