- Pre SC dose 3, 2 hours post SC dose 3, 6 hours post SC dose 3, 12 hours post SC dose 3, 24 hours post SC dose 3, 48 hours post SC dose 3, 1 week post SC dose 3, and 8 weeks post SC dose 3.

Summary statistics and changes from baseline of calculated average for heart rate, PR, RR, QRS, QT, and QT interval corrected for heart rate using Fridericia's formula (QTcF) will be presented by relative time to dose and by each dose.

An outlier analysis will be performed. Summary table showing the frequency and percentage of participants who meet any of the following criteria at each relative time to dose will be produced.

• QT, QTcF interval:

- \circ $\leq 450 \text{ msec}$
- \circ > 450 and \leq 480 msec
- \circ > 480 and \leq 500 msec
- \circ > 500 msec
- QT, QTcF interval increases from baseline:
 - $\circ \le 30 \text{ msec}$
 - \circ > 30 and \leq 60 msec
 - \circ > 60 msec

All ECG findings will be presented in a data listing.

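### Vital-sign and ECG changes after each SC dose are referenced only to the pre-IV value; a supplementary change from the same-day predose reading would be a cheap, minor improvement

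*SAP*

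**What the plan says.** SAP Section 4 gives the general rule, "Baseline will be defined as the last non-missing assessment (including repeated and unscheduled assessments) before the first dose of study drug administration", and allows exceptions where another rule is specified. Section 9.3 specifies none; it plans "Summary statistics and change from baseline for vital signs (temperature, respiratory rate, pulse, and systolic and diastolic blood pressure", all by time relative to dose. Section 9.5 restates the rule for ECG: "The baseline will be defined as the average of the last non-missing assessment (including repeated and unscheduled assessments) before the first dose". ECG changes "will be presented by relative time to dose and by each dose", but the baseline itself is not reset at each dose. The QT/QTcF increase categories in Section 9.5 (up to 30, 30 to 60, above 60 msec) inherit it.

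Protocol Table 3 schedules vital signs and a triplicate ECG before dosing on every dosing day. SAP 9.3 and 9.5 show these readings as Pre SC dose 1, 2 and 3 rows alongside the 2, 6, 12 and 24 h rows. No change from them is planned.

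**The concern.** The primary objective covers tolerability of the IV dose and of the three weekly SC doses. Part of that question is what happens in the hours after an injection. Protocol 8.3.6.2 includes "alterations in heart rate and blood pressure" among the systemic events that can count as an injection-associated reaction within 24 h. Protocol 2.2.2.3 reports that "Heart rate increases were observed in all animals at 1 mg/kg/dose", although those increases stayed within normal variation and were judged not adverse.

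A change measured from a pre-IV value combines three things: the acute effect of that injection, variation between days, and any effect left from earlier doses. The same row also mixes reference ages. At SC dose 1 the reference is 14 days old for the first participant in a cohort and 7 days old for the others. Elsewhere the SAP does separate doses: Section 9.1 assigns adverse events to the route given most recently, and Section 8.3 provides carryover-corrected Cmax and AUCtau for SC doses.

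At stake is how cleanly the spread of the acute change, and any QTcF increase flags, can be read from the tables in cohorts of about five.

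**Working it through.** **Inputs.** Dosing days are from Protocol Table 3: Days 1, 15, 22, 29 (first participant) and Days 1, 8, 15, 22 (subsequent participants). The baseline rule and table rows are from SAP 4, 9.3 and 9.5. Enrolment is about 15, about 5 per cohort. The within-day SD (sw) and between-day SD (sb) of a reading are not in the documents and are assumed below. The plan has no figure of its own to reproduce here.

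**1. Age of the reference on SC dosing days**, when the Day 1 predose reading is available.
- First participant: 15−1 = 14, 22−1 = 21, 29−1 = 28 days.
- Subsequent participants: 8−1 = 7, 15−1 = 14, 22−1 = 21 days.
- The range is 7 to 28 days, for dosing-day readings only.

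**2. What the planned tables can give.** Let B be the pre-IV value.
- Mean: mean(post − B) − mean(pre − B) = mean(post − pre). B cancels, provided the same participants contribute to both rows. SAP 4 does not impute missing data, so the subtraction fails if they differ.
- SD: Var(post − pre) = Var(post − B) + Var(pre − B) − 2Cov(post − B, pre − B). The covariance is not tabulated, so the SD cannot be obtained. The range and the counts above 30 and 60 msec need individual pairs, which appear only in the listings.

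**3. Noise in the planned change, same-day readings (2, 6, 12 h).** Take a reading as person level + day effect (SD sb) + reading error (SD sw).
- From same-day predose, the day effect cancels: variance = 2sw².
- From the pre-IV value: variance = 2(sw² + sb²).
- SD ratio = sqrt(1 + sb²/sw²).

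| Assumed sb²/sw² | SD ratio |
|---|---|
| 0.5 | sqrt(1.5) = 1.22 |
| 1 | sqrt(2) = 1.41 |
| 2 | sqrt(3) = 1.73 |

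These are expected ratios; in one cohort of five the observed SDs can fall either way. The formula does not cover the 24 h row. That reading is on a different day from the predose reading, so the day effect does not cancel.

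**4. Illustration for the QTcF category above 30 msec**, no drug effect, normal errors, sw = sb = 8 msec assumed.
- SD of change: sqrt(2(64 + 64)) = 16.0 msec from pre-IV; sqrt(2 × 64) = 11.3 msec from same-day predose.
- Chance that one reading exceeds 30 msec: P(Z > 30/16.0) = 3.0% versus P(Z > 30/11.3) = 0.4%.
- Readings: 15 participants × 3 doses × 3 times = 135. Expected chance flags: about 4.1 versus 0.5.
- With each SD anywhere from 5 to 10 msec, the per-reading chance is 0.1% to 6.7% versus below 0.01% to 1.7%.

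**5. Is the predose value drug-free?** Probably not. If the half-life is about 6.4 days (an assumption, in line with the Amendment 4 rationale that places EoT at 5.5 half-lives: 35/5.5 = 6.36 and 36/5.5 = 6.55 days), the IV fraction remaining at the first SC dose is 2^(−7/6.4) = 47% for subsequent participants and 2^(−14/6.4) = 22% for the first. For half-lives of 5 to 7 days the ranges are 38% to 50% and 14% to 25%.

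**The case against.** The case for leaving the plan alone is substantial, and most of it stands.

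- Protocol 9.4.2 itself asks for ECG change from a pretreatment baseline, so the SAP follows the protocol. A reader might infer that the baseline is wrong and should be replaced. The documents do not support that. The pre-IV value is the only drug-free reference, and total effect against a drug-free state is what cumulative tolerability needs. An on-drug predose reference used alone could hide a sustained QTcF effect.
- A reader might infer that the acute change cannot be seen at all. That is also too strong. Its mean follows from the planned rows when data are complete, individual values are listed, and the absolute QTcF categories use no baseline.
- A reader might take 7 to 28 days to describe every change after SC dosing. It does not. Vital signs run to Day 85/78 (84/77 days after Day 1) and ECG to Day 65/57 (64/56 days), and a drug-free reference suits that follow-up.
- A reader might turn the SD inflation into lost precision or extra participants. The SAP plans no hypothesis and no confidence interval for these data, and the sample size is empiric.
- The primary endpoint is TEAE and TESAE incidence. Injection-associated reactions are judged by the investigator, not derived from these tables.

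What remains is narrow: the SD, range and increase counts of the acute change are not tabulated, and the planned versions include between-day variation.

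**Conclusion.** The point holds as a cheap improvement of minor severity, not as a fault that threatens the study's conclusions. For the 2, 6 and 12 h readings after SC doses, the planned SD of change is larger than the same-day SD by sqrt(1 + sb²/sw²), for example 1.22 to 1.73 for variance ratios of 0.5 to 2. The QTcF counts above 30 and 60 msec carry the same extra variation. The size rests on assumed SDs and a simple additive model with equal variances on each day; the documents do not show how large day-to-day drift is in these participants. The existing baseline should remain the primary reference for cumulative change and follow-up.

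**What to change.** - **SAP 4:** keep the present baseline and add a supplementary dose-day baseline, defined as the last predose assessment on the same dosing day. The existing allowance for exceptions leaves room for this.
- **SAP 9.3 and 9.5:** add change from the dose-day baseline (mean, SD, range) at 2, 6 and 12 h after each SC dose. The 24 h row is optional; the gain there is only removal of slow drift and earlier-dose effect.
- **SAP 9.5:** add supplementary QT/QTcF counts above 30 and 60 msec against the dose-day baseline, beside the planned counts.
- **Labelling:** mark all of these as acute change only, because the predose value may contain residual drug effect and could mask a sustained one.

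The cost is a few lines of SAP text and one extra set of columns. No new data, visits or protocol change are needed. While editing Section 9.3, note that the quarter-hourly first-hour vital signs in Protocol Table 3 are missing from its schedule and summary times, which start at 2 h. That is a separate gap, which these columns would not close.
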